### 3. Objectives & Specific Aims

**Objective:** This is a formative study to lay the groundwork for establishing a large cohort of incident colon cancer to examine the microbiome-immune relationship in colon cancer outcome. Our hypothesis is that colon cancer treatment, recurrence and survival are compromised by treatment-induced dysbiosis and dependent upon pre-treatment microbial structure. We plan to address this hypothesis with the following aims:

**Aim 1: Determine if the gut microbiome and microbial metabolites are altered in response to cancer treatment and correlate with CID incidence and severity in stage II/III colon cancer**

Sub-Aim1a: Quantify the gut microbiota prior to surgery and treatment, and at 3 time points during FOLFOX, and correlate with CID incidence and severity

Sub-Aim1b: Quantify microbial pathway abundance and fecal metabolite levels prior to, and during treatment, and determine their associations with incidence and severity of CID

Sub-Aim1c: Quantify circulating and tumor tissue cytokine levels prior to, and during treatment, and determine their associations with the gut microbiota, and incidence and severity of CID

**Aim 2: Determine if the dietary history or dietar intake during treatment is associated with CID incidence and severity in stage II/III colon cancer**

Primary outcomes: CID incidence and severity and gut microbiome and metabolome changes. The patients with colon cancer, serving as their own controls, will provide stool samples that enable clinicians to predict toxicity of anti-cancer therapy in stage II/III colon cancer patients.

Secondary outcomes: Circulating cytokines, dietary history and changes during treatment, stool index changes

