## 4. Methodology

### 4.1 Study Design.

While incident colon cancer studies have been conducted, none have integrated the analysis of the microbiome with other clinically relevant factors. With the recent evidence from animal models demonstrating the importance of the microbiome-immune relationship in shaping the efficacy of anti-cancer treatment, a prospective human study is critical to understand how and if these results translate to human colon cancer. In general, however, there is a paucity of prospective human microbiome studies addressing the microbiome-host relationship. Thus, this study design will address several outstanding issues in the fields of cancer and microbial ecology.

In order to understand the causative factors in response to colon cancer treatment and identify predictive biomarkers, and prospective cohort study is necessary. As previously discussed, the outstanding questions that will be answered through this type of study design are 1) whether the initial microbiome/community structure predicts treatment toxicity, and 2) the impact of the diet and microbiome on the immune response during and after cancer treatment, and its resiliency after cessation of treatment. By collecting multiple types of specimens before, during and after treatment with extensive follow up, we will be able to answer the first questions regarding predictive biomarkers that individually or in combination predict response to treatment. We will also be able to use these data to identify mechanisms in the causal pathway of response to treatment that can be used in future studies to improve survival or reduce recurrence.

This will be a large prospective cohort of incident colon cancer. For this protocol, there is no group assignment, randomization or placebo group. Study Day 0 for this protocol will be considered when the patient is diagnosed with colon cancer after consent, and separately Treatment Day 1 is the day on which the patient starts their first chemotherapy infusion (lasting 12 weeks). All stool samples collected will be considered beyond standard of care (SOC), however, all blood samples will be taken as part of SOC, with the exception that an 2 additional vials of blood will be taken for immune marker analysis. Briefly, samples for this project will include:

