#### **4.4 Data Analysis.**

Classification of taxa associated with side effects or severity: Recently, in an animal model of colon tumorigenesis (AOM/DSS), investigators used the initial microbial community structure (16s rRNA sequencing) to predict tumor burden after exposure to various antibiotics during colon carcinogenesis. In order to conduct a similar analysis and reduce data dimensionality, we will first perform cluster modeling using Dirichlet multinomial mixtures (Holmes et al. 2012) to identify microbial clusters (community state types). To determine which taxa or taxonomic cluster are the best predictors of treatment side effects (CID, mucositis) and severity (stage 3-4), we will conduct 10-fold cross-validation using the RandomForest package (Version 3.6.4) in R (R-studio, Version 0.98.1091; Boston, MA). Specifically, 5,000 trees will be used and the parameter mtry will be set at 100. The taxa with the highest importance scores will be used for further analysis. This procedure will be tested by splitting the data into test and training sets, then running Random Forest using the same procedure described above on the training dataset and comparing the predictive accuracy of the top taxa (based on importance scores) in the test set. Based on this 10-fold cross-validation, we will be able to calculate sensitivity and specificity. These top taxa will then be used to generate receiver operator curves (ROC) and calculate area under the curve (AUC). Each microbial cluster or taxa will undergo independent logistic regression testing to calculate area under the ROC curve using Stata (v13). The command roccomp will be used to compare statistical difference between AUCs and determine the best combination of taxa for classification of CID or mucositis and for severity.

Microbiome-Diet Analysis: To evaluate the impact of diet on the stool and tissue microbiome, we will use the dietary analysis generated from the ASA24 and DHQIII, which includes the Healthy Eating Index (HEI). Prior to analysis, we will conduct normality testing for each variable using Shapiro-Wilk test. For any variables that do not pass, a logarithm transformation will be performed. In order to identify any potentially important diet or nutrient-microbiome associations, we will conduct correlation analysis between dietary macronutrients (carbohydrates, fats, proteins) or micronutrients (vitamins and minerals)

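### The taxa combination chosen by AUC comparison is never scored on patients who were not used to choose it, so its AUC would be optimistic

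*Protocol*

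**What the plan says.** Protocol section 4.4 sets out the classification of CID, mucositis and severity in this order.

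1. A random forest is run with 10-fold cross-validation ("5,000 trees will be used and the parameter mtry will be set at 100"), and the taxa with the highest importance go forward.
2. The procedure is tested by a training/test split. The forest is rerun in the training part, and the check consists of "comparing the predictive accuracy of the top taxa (based on importance scores) in the test set".
3. Accuracy figures follow: "Based on this 10-fold cross-validation, we will be able to calculate sensitivity and specificity".
4. Next comes: "These top taxa will then be used to generate receiver operator curves (ROC) and calculate area under the curve (AUC").
5. Then: "Each microbial cluster or taxa will undergo independent logistic regression testing to calculate area under the ROC curve".
6. Last: "The command roccomp will be used to compare statistical difference between AUCs and determine the best combination of taxa for classification of CID". The sentence goes on to mucositis and severity, and the paragraph ends there.

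The test set is mentioned only at step 2, before any combination exists. Steps 4 to 6 name no data set. The later parts of section 4.4 do not return to this choice; the tenfold cross-validation in the metabolite-CID analysis belongs to the PLS-DA model.

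**The concern.** Picking the candidate with the highest AUC also picks the one most favoured by chance in those patients. The winner's AUC is therefore too high unless it is measured again in patients who took no part in the choice. Here the choice is the last step and nothing follows it.

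The figure matters because the protocol promises prediction. Section 4.1 speaks of "predictive biomarkers that individually or in combination predict response to treatment", and section 3 says that the patients "will provide stool samples that enable clinicians to predict toxicity of anti-cancer therapy". The AUC behind the final choice is the number that section 4.4 attaches to a combination. If it is scored on the data that chose it, taxa with no information can look predictive, and a weak signal can look much stronger than it is.

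**Working it through.** The protocol states no AUC, target AUC or power for the classifier, so there is no figure to reproduce. The check has three parts.

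**1. Possible readings of steps 4 to 6**

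- All patients: choice and score share the same data.
- Test set: it becomes a selection set, and no untouched patients remain.
- Training set only: the choice is sound, but it still needs a held-out score, which is not stated.

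Each reading needs an added sentence. The first two give an optimistic AUC.

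**2. Size from order statistics, no true signal**

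Inputs: 112 patients (section 4.3) and CID in half of them (section 2 says over 50%), so 56 with and 56 without. Assumed: a 70/30 split, giving a 34-patient test set with 17 and 17.

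Null SD of an AUC with m events and n non-events: √[(m+n+1)/(12mn)].

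- Test set: √[35/(12×17×17)] = 0.100.
- All patients: √[113/(12×56×56)] = 0.0548.

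Best of k retained taxa on the test set, direction fixed in training: 0.5 + E(max of k normals) × 0.100.

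- k = 3: 0.5 + 0.846×0.100 = 0.585
- k = 5: 0.5 + 1.163×0.100 = 0.617
- k = 10: 0.5 + 1.539×0.100 = 0.655

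Best of p taxa on all patients, either direction: 0.5 + E(max of p absolute normals) × 0.0548.

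- p = 100: 0.5 + 2.747×0.0548 = 0.651
- p = 300: 0.5 + 3.092×0.0548 = 0.669
- p = 1,000: 0.5 + 3.435×0.0548 = 0.688

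**3. Simulation of the procedure, no true signal**

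The main run used 112 patients, 56 events, 5,000 trees and mtry 100, with 150 repetitions. Assumed: 300 taxa (mtry 100 needs at least 100), the top 5 retained, a 70/30 split, and a rule that starts from the best taxon and adds another only if the AUC comparison gives p<0.05. Sensitivity runs used 1,000 trees and 100 repetitions (40 for the top 10).

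| Setting | Chosen and scored on all | Chosen on test set | Fixed in training, scored once | All top taxa in one model, all patients |
|---|---|---|---|---|
| Main run | 0.671 | 0.619 | 0.487 | 0.783 |
| Top 3 | 0.667 | 0.581 | 0.500 | 0.733 |
| Top 10 | 0.674 | 0.667 | 0.505 | 0.854 |
| 100 taxa | 0.648 | 0.618 | 0.488 | 0.746 |
| 1,000 taxa | 0.693 | 0.619 | 0.517 | 0.812 |
| 50/50 split | 0.671 | 0.587 | 0.491 | 0.778 |
| 22 events (20%, assumed) | 0.692 | 0.643 | 0.504 | 0.787 |

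Correlated or skewed taxa gave similar results (0.668 and 0.665 on all patients; 0.618 and 0.613 on the test set). The first two columns agree closely with the order-statistic values in part 2.

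In the main run on all patients the rule kept 1.05 taxa on average. Its AUC of 0.671 compares with 0.668 for the best single taxon, so nearly all the optimism comes from ranking and picking one taxon.

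With a weak true signal (5 of 300 taxa shifted by 0.4 SD), the choice on all patients showed 0.695 against 0.560 in new patients. Chosen on the test set, it showed 0.644 against 0.540. Fixed in training and scored once, it showed 0.526 against 0.539 (SE 0.015).

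A second simulation used other assumptions: 92 taxa, ranking by single-taxon AUC, best subset of up to three from eight, and 100 or 112 patients. The chosen AUC exceeded the AUC in new patients in all 16 settings.

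**The case against.** The strongest reply is that section 4.4 does not say the AUC comparison runs on all patients. The partition feeding an AUC is a detail that a SAP, not shown here, may fix. The sentences are also not strictly sequential: the one on sensitivity and specificity refers back to the cross-validation. The ROC steps could therefore be describing how accuracy is compared in the test set.

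Part of this stands. A reader might infer that the protocol commits to scoring on all patients; it does not. But if the ROC steps take place in the test set, that set makes the choice and its AUC is still optimistic, though less so (0.619 rather than 0.671 in the main run). The point also does not rest on missing detail alone. The protocol fixes a selection rule, its software and an order that ends in selection, so a SAP would have to add a step.

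A reader might also infer that the whole prediction analysis is unvalidated. It is not. The random forest has a cross-validation and a test split, and those figures stand beside the AUC. They validate the importance ranking, not the later choice.

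A third tempting inference is that the AUC comparison alone inflates the result to about 0.8. The values of 0.73 to 0.85 arise when several top taxa are put into one model and scored on all patients, which is a different rule.

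Finally, section 3 calls the study formative and no AUC is an endpoint. This limits the consequence but does not remove it, given the predictive claims in sections 3 and 4.1.

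**Conclusion.** The point holds, as something that should be changed. As written, the plan offers no unbiased AUC for the taxon or combination it finally selects, for CID, mucositis or severity.

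Under no true signal, with 112 patients, the selected AUC averages about 0.65 to 0.69 on all patients and 0.58 to 0.67 if chosen on the test set, against about 0.50 when scored once on held-out patients. One model with several top taxa, scored on all patients, shows about 0.73 to 0.85.

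The direction follows from the procedure. The size rests on assumptions that the protocol does not supply: 100 to 1,000 taxa, 3 to 10 retained, a 70/30 or 50/50 split, and the rule for adding taxa. Confidence in the size is therefore moderate.

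**What to change.** State in section 4.4 that importance ranking, logistic fitting and the choice by AUC comparison are done only in the training set of the split already planned, or inside each outer fold of a nested cross-validation. Report the AUC with its confidence interval, the sensitivity and the specificity of the final combination only from held-out predictions.

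This costs wording and analysis code, with no extra patients or samples. The reported AUC will be lower and imprecise. With no signal, a single score on a 34-patient hold-out had an SD of about 0.10 (5th to 95th percentile 0.34 to 0.65). Nested 10-fold cross-validation was only slightly tighter (SD 0.09; 0.37 to 0.66).

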Answers to these important question, can be used to not only enrich our understanding of the mechanisms important to the microbiome-immune system relationship, but will directly inform future decision in colon cancer treatment. Most important, these results may uncover potential therapeutics for cancer treatment and side-affect mitigation, such as chemotherapy-induced diarrhea, which affects over 50% of patients undergoing anti-cancer therapy for CRC. For example, it may be prudent to first restructure the microbiome to establish a more conducive environment prior to treatment to enable the most effective treatment response. Further, it may be possible to leverage the immune system by engineering probiotics that deliver anti-inflammatory cytokines that ameliorate inflammation after treatment. **Conducting this study is a significant part of the key steps in elucidating causal mechanisms underlying the impact of the microbiome-immune system relationship on efficacy of anti-cancer therapy, and determining the impact of diet and metabolite fluctuations in predicting recurrence and survival.**

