### **Sample Population:**

Inclusion/exclusion criteria – the study population will be derived from the two participating BSW hospital systems (Waco and Temple, TX) and will be selected to participate in the study on the basis of the following criteria (inclusion): Age  $>18$  and  $\leq 79$  years, written informed consent, ability to perform informed consent, FOLFOX treatment and Stage II/III colon cancer diagnosis. To ensure fitness for recurrence detection and anti-cancer therapy, the age was restricted to  $>18$  so as not to include minors, and  $\leq 79$  years based on life expectancy with colon cancer diagnosis. Individuals will be excluded from participating if any of the following criteria are met: not diagnosed with stage II or III colon cancer, pregnancy, Lynch syndrome or FAP diagnosis, inability or refusal to perform informed consent, inability to comply with the follow-up program, history of previous colon cancer diagnosis, previous treatment with antibiotics in the last month, previous bowel resection.

Sample size - Based on current data from BSW, the recurrence rate for stage II/III colon cancer is 20%, with a 10% 5-year survival rate for stage IV colon cancer. Given our study design, we conducted power calculations for each group. To meet the number required to detect chemotherapy induced diarrhea and mucositis associated with microbial and metabolite abundance, we need to collect at least 560 stool samples from 112 people (Observational Study). To meet the power requirements for detection of differentially abundant microbes and metabolites associated with chemotherapy-induced CID we estimate needing at least 100 stage II/III patients. The specific power calculation for these groups are provided below.

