### Taxonomic differential abundance analysis

Power calculations for differential abundance analysis in human microbiome studies can be challenging, as there is limited data with highly consistent sample preparation available and uncertainty in the overall distribution of bacterial taxa throughout the human population. Recently, a CRC stool-based microbiome study of a large cohort was performed by Baxter and colleagues. This publicly available data serves as a potential resource for power-analyses by allowing for empirical calculation of the expected variability of taxa in both healthy and CRC-associated gut microbiomes.

We obtained the raw 16S rRNA sequence data from the Baxter study including patients with CRC (n=120) and healthy controls (n=172). After preprocessing and subsampling high-quality reads to an equivalent depth of 10,000 per sample, we identified 92 genus-level groups that each represented (on average) at least 0.25% of sequences from the CRC or healthy patient groups. We then computed the corresponding variance in relative abundance for each of these 92 taxa, and used the empirical values to perform a comprehensive power-analysis.

As expected, increased statistical power was found with higher abundance genera, so here we focus on power results for organisms reflecting an average of 0.25-1.0% of 16S sequences in the gut microbiome because detecting differences in these rare taxa may be critical to our study. Among the genera found at this low level, if we assume equal variance in two normally-distributed populations and require a significance level of  $\alpha=0.05$ , we expect that with a comparison of 40 vs 100 individuals, we will be able to detect a relative increase of 200% (e.g. 0.5% mean abundance increased to 1.5%), with a statistical power of 92.3% (*pwr.t2n.test* in R).

Considering the genera with average frequency  $>1\%$ , we estimate that with a 40 vs 100 sample comparison, we will be able to detect a relative increase of 200% (e.g. 1% mean abundance increased to 3%, or 2% mean abundance increased to 6%), with an expected statistical power of 99.6%.

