The REA will pre-screen patients that are scheduled to undergo colonoscopy to identify patients as a potential study participant. Patients scheduled to undergo colonoscopy for suspected colon cancer will be approached by the REA or Physician to ask if they would like to participate in the study and enrolled if they give consent. These informational sources will provide a short description of the study purpose and requirements for participation. Written informed consent will be obtained by the REA from patients agreeing to participate in the study and before commencement of any study activities. Once identified, the REA will screen the patients and obtain consent for study entry. After consent, participating patients will be provided with a study identification number. This number will be utilized on the data collection form, sample labeling and dietary assessments to promote confidentiality throughout the study procedures. At the consent visit, patients will complete a data collection form utilized to confirm study eligibility and record interval history at the sampling time points. Next, they will be given a stool collection kit to take home along with their bowel prep kit, to collect stool prior to bowel prep. If a positive CRC diagnosis is made through the pathology department and confirmed by GI physicians at BSWH facilities, they would continue as a participant in study. This method will allow the collection of stool specimen prior to colonoscopy. **If they are not diagnosed with stage II/III CRC, subjects will be asked if the stool sample can be used in the study as a control. Subjects will be given the option to agree or decline on the prescreening consent form.** [name] will direct the longitudinal specimen collections, assessments and retention. This consent information will be kept at BSWH by either the REA in a password protected file only accessible by the REA or [name]. We plan to recruit 112 stage II/III patients, (110% of what is needed according to power calculations). Recruitment and sample collection will be supported by the clinical practice sites in Temple and Waco, REAs, and facilitated by Principle Investigator [name] PhD, MPH, RD and Physician Drs. [name].

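### roccomp is assigned to choose the best combination of taxa, but its p-value is not a reliable basis for that choice unless the compared models are fixed in advance and scored out of sample, which the protocol does not say

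*Protocol*

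**What the plan says.** The paragraph on classifying taxa in Protocol section 4.4 sets out a sequence of steps.

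- A random forest with 10-fold cross-validation ranks the taxa, and "The taxa with the highest importance scores will be used for further analysis".
- A check on held-out data is described for that step: "This procedure will be tested by splitting the data into test and training sets".
- ROC curves and AUCs are then produced for the top taxa. "Each microbial cluster or taxa will undergo independent logistic regression testing to calculate area under the ROC curve using Stata (v13").
- Finally, "The command roccomp will be used to compare statistical difference between AUCs and determine the best combination of taxa for classification of CID", and likewise for mucositis and for severity.

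The section does not describe how a multi-taxon model is built, which patients the roccomp step uses, or what significance level applies to it. It names no other rule for choosing the combination.

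**The concern.** roccomp tests whether two given scores, measured on the same patients, have equal AUC. Its normal reference distribution suits two distinct scores that were not estimated from those patients. Choosing a combination asks something else: does A+B classify better than A? Those logistic models are nested. If B adds nothing, its fitted coefficient is close to zero, the two fitted scores nearly coincide and the AUC difference degenerates, so the normal reference fails.

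The choice matters because whether the microbiome predicts treatment toxicity is one of the questions the study design is built on (section 4.1), and CID incidence and severity are primary outcomes (section 3). The taxa carried into the planned larger cohort would depend in part on this rule.

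**Working it through.** The protocol gives no AUC, AUC difference or power for this step, so there is no figure to reproduce. The check is by simulation.

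**Inputs from the protocol**
- Sample size: "We plan to recruit 112 stage II/III patients" (Subject recruitment and enrollment); sensitivity run at 100, from "we estimate needing at least 100 stage II/III patients" (Sample Population).
- CID frequency: "chemotherapy-induced diarrhea, which affects over 50% of patients undergoing anti-cancer therapy for CRC" (section 2). 50% was used, with 20% and 30% as sensitivity.
- Group sizes in the power section: "we expect that with a comparison of 40 vs 100 individuals", that is n = 140 with 40/140 = 29% cases.
- Candidate taxa: 92 genera (Taxonomic differential abundance analysis).

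**Assumptions**
- Two-sided 0.05. The protocol states 0.05 only for the differential-abundance calculation.
- Independent normal taxa, with the effect sizes shown below.

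**Tests compared**, both on the patients used for fitting:
- Correlated-AUC (DeLong) test: z = (AUC_AB − AUC_A) / √(V_A + V_AB − 2C), referred to the standard normal.
- Likelihood-ratio test (LRT): G = 2(ℓ_AB − ℓ_A), referred to chi-square with 1 df.

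**Result 1: log-odds scale.** n = 112, 50% CID, base taxon log-odds 0.8 per SD. Rejection rates in 2,000 replicates, with a separate run in brackets:

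| Added taxon, log-odds | AUC test | LRT | LRT − AUC test |
|---|---|---|---|
| 0 | 0.2% (0.2%) | 5.4% (4.9%) | size |
| 0.5 | 12.5% (10%) | 67.7% (68%) | 55.2 points |
| 0.65 | 26.6% (26%) | 87.2% (89%) | 60.6 points |
| 0.8 | 49.7% (49%) | 96.6% (96%) | 46.9 points |

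The last column uses the first run. The Monte Carlo standard error is at most √(0.5 × 0.5 / 2000) = 1.1 points. With 30% CID and added log-odds 0.65, power is 23.8% against 84.2%.

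**Result 2: standardised-difference scale.** n = 112, 50% CID. A marker with standardised difference d has AUC = Φ(d/√2), so base d = 0.35 gives 0.60 and base d = 0.74 gives 0.70. AUC test against LRT:

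| Added d | Base AUC 0.60 | Base AUC 0.70 |
|---|---|---|
| 0 | 0.2% vs 5.1% | 0.3% vs 6.5% |
| 0.3 | 5.2% vs 36.1% | 2.4% vs 31.4% |
| 0.5 | 21.8% vs 74.4% | 11.7% vs 67.3% |
| 0.74 | 62.5% vs 97.6% | 42.7% vs 94.8% |
| 1.0 | 93.2% vs 100% | 82.8% vs 99.9% |

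With 20% CID and base AUC 0.70, d = 0.5 gives 6.9% vs 51.8%. At n = 100 (50% CID) and n = 140 (29% CID), size is 0.1-0.4%, and power at d = 0.5 is 11-24% vs 65-76%.

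**Result 3: other readings the text leaves open**

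1. *Single-taxon AUCs compared with each other.* These scores are non-nested and fixed. Two equal markers (d = 0.5 each) give a size of 4.9%, so roccomp is valid.
2. *Models fitted on training patients and compared on test patients* (base AUC 0.70). Size is 5.3% with a 56/56 split and 4.1% with 75/37, but only 0.5% of runs reject in favour of the larger model. Power for d = 0.74 is 24% and 15%.
3. *Top-ranked null taxa among 92, ranked on the same patients and added to a base marker.* The AUC test rejects in 5-14% of runs when one is added, 62-84% for three and 90-98% for five.

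**The case against.** The strongest defence is that the text never describes adding B to A, a stopping rule, or dropping a taxon because of a non-significant p-value. It describes separate single-taxon regressions, for which roccomp is sound, and it provides for cross-validation and a training/test split. Such details are often left to the SAP. This stands in part. Nesting and same-patient scoring are inferences, and the figures for that case are conditional on them.

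The defence does not remove the point. The protocol itself gives roccomp the task of determining a combination, and comparing single-taxon AUCs cannot do that. The split is described for the random forest; the later ROC, logistic and roccomp sentences name no held-out set. If one were used, size would be acceptable but power low.

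A reader might infer that roccomp almost never rejects and that real contributors will therefore be dropped. The documents do not support that. Near-zero rejection applies to null or weak taxa: for strong ones (d = 1.0) the test rejects in 55-93% of runs across the settings tried. Taxa also reach this step after importance ranking, and ranking on the same patients can turn the error into false inclusion.

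A reader might also infer that substituting a likelihood-ratio test is enough. It is not. After ranking 92 null taxa on the same patients, that test accepts the top null taxon in about 88% of runs, against about 5% for the AUC test (base log-odds 0.8, n = 112).

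Finally, the study calls itself formative, and random-forest importance and test-set accuracy also inform which taxa matter. That limits the consequence but does not justify the rule.

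**Conclusion.** Wrong as written: roccomp is given a selection task for which its p-value is unreliable. For nested models fitted and compared on the same patients without prior ranking, size is about 0.2% instead of 5%, and moderate contributors lose roughly 55-60 points of power against the likelihood-ratio test at n = 112. With prior ranking on the same patients, null taxa can pass often, especially several together. The p-value can therefore mislead in either direction, and no net bias toward smaller or larger combinations can be claimed.

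The sizes rest on assumed effects, independent normal taxa and a 0.05 level; real taxa are correlated and skewed. roccomp stays valid for comparing non-nested, fixed scores such as single-taxon AUCs.

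**What to change.** In the classification paragraph of section 4.4:

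- Stop using roccomp to choose the combination. Choose it by penalised logistic regression. A likelihood-ratio test is acceptable only for a taxon in a nested model specified without looking at the same patients' outcomes.
- Carry out all selection, including the random-forest importance ranking, inside the training folds.
- Report the AUC and the AUC difference, with intervals, from held-out patients as descriptive measures.
- Keep roccomp only for non-nested scores fixed before they are applied to the patients being compared.

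The cost is protocol or SAP wording and a few lines of code, with no new data. AUC differences lose their p-value as the selection criterion, and with about 112 patients the held-out intervals will be wide.
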